3.4 Cabozantinib

Cabozantinib (also known as XL184) is an oral tyrosine kinase inhibitor that targets VEGFR2, c-MET, AXL, and other RTKs with half maximal inhibitory concentration (IC₅₀) in the low nanomolar range [25]. Clinical activity with cabozantinib has been demonstrated in a range of tumor types, including advanced hepatocellular carcinoma, renal cell carcinoma and medullary thyroid cancer where the drug is now FDA approved [26-30]. The predicted terminal half life of cabozantinib at the approved dose of 60mg daily in RCC patients was 99hrs [Investigator's

Brochure version 14]. Of note, different pharmacokinetics was observed in medullary thyroid cancer patients. Cabozantinib is also highly protein bound in human plasma ($\geq 99.7\%$).

Cabozantinib has previously been studied in melanoma patients as cohort in a larger phase 2 randomized discontinuation trial (RDT) [9]. A total of 77 patients with advanced melanoma (62% cutaneous melanoma) were treated with cabozantinib at 100mg daily for a 12 week lead in period. Patients with stable disease after 12 weeks were randomized to either continue on cabozantinib or discontinue and evaluate for progression free survival (those patients with partial or complete responses would stay on drug). At week 12, the ORR was 5%; however 55% of patients with evaluable disease demonstrated some tumor regression (refer to Figure 3-1). Of the 26 patients with stable disease and randomized to stay on treatment or discontinue, the median PFS was 4.1 months versus 2.8 months (HR 0.59, P=0.284). The median overall survival of the entire cohort was 9.4 months.

[figure not shown]

Figure 3-1. Best change in tumor response (RECIST) at week 12 from baseline on the Phase 2 RDT of cabozantinib in patients with advanced melanoma. N=64 for evaluable patients.

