5.0 STUDY DESIGN

5.1 Overall Schema

Subjects with unresectable advanced melanoma meeting eligibility criteria (refer to Section 6.0) will be screened for participation on the protocol. The screening phase will include obtaining baseline imaging studies, labs, history & physical, EKG, and collection of a fresh tumor biopsy or archived tumor specimen (refer to Table 7-1). Once meeting eligibility criteria and enrolled on study, subjects will begin treatment with nivolumab/ipilimumab and cabozantinib starting on day 1 of cycle 1. The treatment schedule and follow up is outlined further in the schema Figure 5-1 and Table 7-1. Patients who attain confirmed response or stable disease and are able to tolerate study drugs will continue treatment for up to 2 years. Discontinuation after 1 year but prior to 2 years will be permitted at the discretion of the treating investigator in patients with disease control achieving either a complete or partial response.

Figure 5-1. Treatment Schema

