5.2 Study Drug Dosing

Induction phase:

Nivolumab 3mg/kg IV plus Ipilimumab 1mg/kg IV every 3 weeks x 4 cycles (12 week period)

Cabozantinib 40mg PO daily for 12 weeks

When nivolumab and ipilimumab are to be administered on the same day during the induction phase, nivolumab is to be administered first over 30 minutes. Nivolumab infusion must be promptly followed by a saline flush to clear the line of nivolumab before starting the ipilimumab infusion. The second infusion will be the ipilimumab over 30 minutes and will start after the infusion line has been flushed, filters changed, and participant has been observed to ensure no infusion reaction has occurred. The time in between infusions is expected to be approximately 30 minutes but may be more or less depending on the situation. Infusion window of -5 minutes/+ 10 minutes for each study drug.

Cabozantinib is an oral tablet taken by the patient daily. Participant is to self administer at the same time every day +/- 1 hour window. Participant is not to eat for at least 2 hours before and at least 1 hour after taking the medication.

A window of ± 3 days may be applied to all study visits.

Maintenance phase:

Nivolumab 480mg IV every 4 weeks for up to 92 weeks

Cabozantinib 40mg PO daily for up to 92 weeks

Maintenance therapy will continue for up to 92 weeks to complete 2 years total of treatment if tolerating therapy well and disease is controlled.

Nivolumab is administered over a 30 minute infusion without any premedication unless there is a prior history of infusion reaction. Nivolumab infusion must be promptly followed by a saline flush to clear the line of nivolumab. Participant is to be observed following infusion to ensure no infusion reaction has occurred.

Cabozantinib is an oral tablet taken by the patient daily. Participant is to self administer at the same time every day +/- 1 hour window. Participant is not to eat for at least 2 hours before and at least 1 hour after taking the medication.

A window of ± 3 days may be applied to all study visits.

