5.3 Biospecimen collection

Baseline tumor collection

Prior cycle 1 of study, all patients must have either an archived tumor specimen available or a fresh biopsy for confirmation of disease and correlative studies. Fresh tumor biopsies may be core needle, punch, or incisional/excisional biopsy. Patients without a safe site of biopsy (as assessed by treating provider) or archived specimen will be exempt from this requirement and may obtain a waiver from the principal investigator after discussion. **Refer to lab manual for specific details on handling, processing and storage.**

On treatment tumor collection

Fresh tumor collection at week 13 (refer to Table 7-1) will be optional in patients with a palpable superficial tumor in the skin, subcutaneous tissue or lymph node. This can be a core needle biopsy, punch biopsy, or incisional/excisional biopsy. Patients without a safe site of biopsy (as assessed by treating provider) will not be considered eligible for the optional biopsy. **Refer to lab manual for specific details on handling, processing and storage.**

At progression tumor collection

Fresh tumor collection at time of progression (refer to Table 7-1) will be optional. This can be a core needle biopsy, punch biopsy, or incisional/excisional biopsy. **Refer to lab manual for specific details on handling, processing and storage.**

Peripheral blood biospecimen collection

Blood samples for study of serum, peripheral blood mononuclear cells (PBMCs), and other components will be collected. Samples will be processed using standard protocols and stored at -

80 degrees Celsius for future analyses. **Refer to lab manual for specific details on handling, processing and storage.**

Stool biospecimen collection

Baseline stool samples will be collected from patients at the start of treatment. Patients will be given a stool kit (Omnigene®-Gut tube, and collection materials including a toilet hat and tool for stool transfer). Patients will need to provide the sample on day 1 of the first cycle (+/- 7 day window). **Refer to lab manual for specific details on handling, processing and storage.**

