8.2.4.1 Cabozantinib Adverse Events

The most frequent AEs experienced by $\geq 20\%$ of subjects treated with cabozantinib in descending order of frequency were diarrhea, fatigue, decreased appetite, nausea, weight decreased, PPES, vomiting, constipation, hypertension, dysgeusia, dysphonia, asthenia, and dyspnea. For a full description of the safety profile of cabozantinib, refer to the Cabozantinib Investigator's Brochure.

Other medically important but less frequent AEs including arterial thrombotic AEs (eg, transient ischemic attack [TIA], and myocardial infarction [MI]) and venous thrombotic AEs (eg, deep vein thrombosis [DVT] and pulmonary embolism), severe hemorrhagic events, proteinuria, wound healing complications, gastrointestinal (GI) perforation, abscesses including intra-abdominal and pelvic abscess, GI and non-GI fistula formation, osteonecrosis, and reversible posterior leukoencephalopathy syndrome (RPLS).

Adverse events associated with laboratory abnormalities experienced by $\geq 5\%$ of subjects treated with cabozantinib in descending order of frequency were anemia, AST increased, ALT increased, hypothyroidism, hypokalemia, hypomagnesemia, thrombocytopenia, hypocalcemia, hypophosphatemia, lactate dehydrogenase (LDH) increased, lipase increased, neutropenia, hyponatremia, ALP increased, leukopenia, and hyperglycemia.

Adverse events may occur within the first few weeks in the course of treatment with cabozantinib, as cabozantinib is expected to reach steady state exposure at approximately 2 weeks following first dose. Events that generally have an early onset include hypocalcemia, hypokalemia, thrombocytopenia, hypertension, PPES, abdominal pain, mucosal inflammation, constipation, diarrhea, and vomiting. Adverse events should be managed with supportive care at the earliest signs of toxicity. Dose reductions and treatment interruptions should be considered. Dose reductions are recommended for events that, if persistent, could become serious or intolerable (Section 8.2.2).

Cabozantinib should be discontinued for the following AEs: visceral perforation or fistula formation, severe hemorrhage, serious arterial thromboembolic events, nephrotic syndrome, hypertensive emergency, persistent uncontrolled hypertension despite optimal medical management, and RPLS.

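### The only stool sample is labelled baseline, yet its window allows collection up to a week after treatment starts

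*Combined protocol and SAP*

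**What the plan says.** Section 5.3, under stool collection, describes the specimen this way: "Baseline stool samples will be collected from patients at the start of treatment". It then sets the timing: "Patients will need to provide the sample on day 1 of the first cycle (+/- 7 day window"). Footnote 7 of Table 7-1 repeats that rule. The table has one stool entry, in the week 1 day 1 column, and none afterwards.

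Treatment starts on the same day. Section 5.1 states that "subjects will begin treatment with nivolumab/ipilimumab and cabozantinib starting on day 1 of cycle 1", and section 5.2 gives the oral drug in induction as "Cabozantinib 40mg PO daily for 12 weeks".

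On early effects of cabozantinib, section 8.2.4.1 says that "Adverse events may occur within the first few weeks in the course of treatment with cabozantinib" and that "cabozantinib is expected to reach steady state exposure at approximately 2 weeks following first dose". It adds: "Events that generally have an early onset include hypocalcemia, hypokalemia, thrombocytopenia, hypertension, PPES, abdominal pain, mucosal inflammation, constipation, diarrhea, and vomiting".

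Section 7.6.1 mentions the gut microbiome as possibly important for anti-tumor immunity and plans 16S rRNA sequencing, or an equivalent, of the stool.

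**The concern.** A baseline biomarker should describe the patient before treatment. If some samples come from before the first dose and others from up to a week after it, the measurement mixes the patient's starting state with whatever the drugs, early bowel symptoms or their management have done. Any comparison of the microbiome with outcome would then be harder to read as a statement about baseline.

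The plan applies a stricter rule to its other baseline specimen. Section 5.3 requires tumor tissue to be in place before cycle 1. Inclusion criterion 4 in section 6.0 and footnote 1 of Table 7-1 accept archived tissue only if no treatment came in between. The stool rule departs from that principle without giving a reason.

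With no second stool sample, there is also no within-patient comparison that could show how far a late sample had moved.

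**Working it through.** The plan gives no figure on this point to reproduce. The check is a day count, a reading of the passages side by side, and one illustrative calculation.

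**1. Day count.** The nominal time is cycle 1 day 1 and the window is 7 days either way. The upper limit is day 1 + 7 = day 8. First doses of all three drugs are on day 1 (section 5.1).

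**2. Doses received by the upper limit.**
- Nivolumab and ipilimumab are given every 3 weeks (section 5.2), so one infusion of each.
- Cabozantinib is daily from day 1, so 7 doses on days 1 to 7, or 8 if the day 8 dose comes before the sample.

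**3. Is there a pre-dose condition anywhere?** None appears in section 5.3, Table 7-1 or footnote 7. Even a sample taken on day 1 itself is not required to precede the infusions. The half of the window before day 1 is pre-treatment; the half after it is not.

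**4. How far into treatment is day 8?** As an illustration, take the half-life in section 3.4: "The predicted terminal half life of cabozantinib at the approved dose of 60mg daily in RCC patients was 99hrs". Under simple accumulation, the fraction of steady state after time t is 1 − 0.5^(t / half-life), with t = 7 × 24 = 168 h:

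| Half-life | Source | Fraction of steady state at 7 days |
|---|---|---|
| 72 h | assumed | 1 − 0.5^(168/72) = 0.80 |
| 99 h | section 3.4 | 1 − 0.5^(168/99) = 0.69 |
| 120 h | assumed | 1 − 0.5^(168/120) = 0.62 |

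At 14 days the 99 h figure gives 1 − 0.5^(336/99) = 0.905, which fits the protocol's own estimate of about two weeks to steady state. The calculation supports one statement only: a patient sampled at the late end of the window is on treatment in a real sense. It concerns plasma drug and does not measure any change in stool.

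**5. What else can fall inside the window?** Section 8.2.4.1 names both diarrhea and constipation among early-onset events. Table 8-4 manages diarrhea with antidiarrheal agents, dietary change and, in some cases, antibiotics. Any of these could precede a sample taken after day 1.

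**6. What depends on the sample?** The microbiome is not among the objectives and endpoints in section 4. Section 11 names tumor mutational burden and PD-L1 and leaves the remaining analyses descriptive and exploratory. No decision rule, efficacy endpoint or safety summary uses the stool data.

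**The case against.** The strongest reply is that very little depends on this sample. The microbiome work has no stated model or endpoint and lies outside section 4. That stands, and it limits the severity.

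Several stronger readings are tempting, and the documents do not support them.

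- **That the microbiome is a specified baseline predictor of efficacy.** Section 7.6.1 speaks generally of comparing baseline and on-treatment variables with response, PFS and OS. It does not tie the stool data to a particular comparison. Such a comparison is likely, but it is not laid down.
- **That the size of the bias can be read from the drug figures.** The 69% above is plasma accumulation, from a half-life predicted for 60 mg in renal cell carcinoma. This trial gives 40 mg in melanoma, and section 3.4 notes different pharmacokinetics in another tumor type. The 15/18 (83%) with diarrhea in the phase 1 study of the triple combination (Table 3-3) is any grade at any time. It says nothing specific about the first week.
- **That a known number of samples is affected.** The documents give no share of late samples. An assumed 10% to 30% of 27 subjects would be 2.7 to 8.1, or about 3 to 8 samples, but this only restates the assumption.
- **That mixed timing would create a false association.** It could do so if collection time or early toxicity were related to outcome, which is not shown. Otherwise the main effect would be added noise.
- **That the problem could not be handled later.** If the collection date is known, a late sample can be flagged or excluded.

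The lab manual, which is not among the documents, might ask for pre-dose collection or record the time. Section 5.3 refers to it only for handling, processing and storage, and the protocol window itself still permits day 8.

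**Conclusion.** The point holds as a minor design flaw. Following the plan exactly can yield an on-treatment stool sample labelled baseline, and no later sample is scheduled against which to judge it. This follows directly from the window and the treatment start date and needs no assumption.

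That treatment, early bowel symptoms or their management would alter the microbiome within a week is a reasonable inference, not a statement in the documents. The size of any effect, and the number of patients sampled late, cannot be estimated from them. Only the exploratory microbiome analysis is affected. The 1-year PFS test, the secondary endpoints and the safety results are not.

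**What to change.** In section 5.3 and in footnote 7 of Table 7-1, change the window to day -7 through day 1, before the first dose of any study drug. Hand out the stool kit at screening, which Table 7-1 already places between day -14 and day 0, so no visit is added.

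Record the date and time of collection relative to the first dose. State in section 7.6.1 or section 11 that samples taken after the first dose are left out of the main baseline microbiome analysis, or are flagged and used only in a sensitivity analysis. For patients already enrolled, the same flagging can be applied wherever the collection date is known.

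The cost is a short wording change in two places, one recorded item and one analysis rule. The downside is that a few late samples drop out of the main baseline analysis of an already small set (up to 27 subjects). The flag-and-sensitivity option keeps those samples in use.

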5.4 Study Treatment Discontinuation

Subjects may discontinue study treatment or withdraw their consent to participate in the study at any time without prejudice. The investigator may withdraw a subject from study treatment or from the study if, in his or her clinical judgment, it is in the best interest of the subject or if the subject cannot comply with the protocol.

In addition, any of the following conditions require discontinuation of the subject from study treatment:

- An AE or intercurrent illness that in the opinion of the investigator warrants the subject's withdrawal from study treatment;
- The investigator believes it is not in the best interest of the subject to continue on study
- Specific conditions described in the Management of Adverse Events Sections 8.2.4.1;
- Necessity for treatment with other anticancer treatment prohibited by protocol;
- Sexually active subjects who refuse to use medically accepted barrier methods of contraception (eg, male condom, female condom) during the course of the study and for 4 months after discontinuation of study treatment;
- Women who become pregnant or are breastfeeding;
- If the subject does not recover from his or her toxicities to tolerable Grade ≤ 2 within 6 weeks, the subject will have study treatment discontinued unless there is unequivocal evidence that the subject is benefitting. In this situation, a subject may be able to restart therapy with a dose reduction upon resolution of the toxicity and with agreement of the principal investigator / Sponsor;
- Request by regulatory agencies for termination of treatment of an individual subject or all subjects under the protocol;
- Significant noncompliance with the protocol schedule in the opinion of the investigator;
- Subjects who cannot tolerate the minimum protocol-specified dose of study treatment will have study treatment discontinued;
- Progressive disease (PD) or the subject no longer experiences clinical benefit as determined by the investigator

6.0 INCLUSION/EXCLUSION CRITERIA

To be eligible for the study the subject must meet all of the inclusion and none of the exclusion criteria:

Inclusion Criteria

1. All patients must have unresectable stage IIIb-IIIId or IV melanoma by AJCC 8th edition.
Note: Patients with uveal melanoma are excluded from this study.
2. Age \geq 18 and ECOG Performance Status of 0 or 1.
3. Measurable disease by imRECIST.
4. Baseline tumor specimen available – either archived tumor specimen collection within the past year and no intervening treatment or fresh tumor collection (A waiver may be considered for the baseline biopsy requirement after discussion with study principal investigator).
5. Recovery to baseline or \leq Grade 1 CTCAE v4 from toxicities related to any prior treatments, unless AE(s) are clinically nonsignificant and/or stable on supportive therapy.
6. Adequate organ and marrow function, based upon meeting all of the following laboratory criteria within 14 days before first dose of study treatment:
 - a. Absolute neutrophil count (ANC) \geq 1500/mm³ (\geq 1.5 GI/L) without granulocyte colony-stimulating factor support.
 - b. White blood cell count \geq 2500/mm³ (\geq 2.5 GI/L).
 - c. Platelets \geq 100,000/mm³ (\geq 100 GI/L) without transfusion.
 - d. Hemoglobin \geq 9 g/dL (\geq 90 g/L).
 - e. Alanine aminotransferase (ALT), aspartate aminotransferase (AST), and alkaline phosphatase (ALP) \leq 3 \times upper limit of normal (ULN). ALP \leq 5 \times ULN with documented bone metastases.
 - f. Total bilirubin \leq 1.5 \times ULN (for subjects with Gilbert's disease \leq 3 \times ULN).
 - g. Serum albumin \geq 2.8 g/dl.
 - h. Serum creatinine \leq 2.0 \times ULN or calculated creatinine clearance \geq 30 mL/min (\geq 0.5 mL/sec) using the Cockcroft-Gault equation:
Males: $(140 - \text{age}) \times \text{weight (kg)} / (\text{serum creatinine [mg/dL]} \times 72)$
Females: $[(140 - \text{age}) \times \text{weight (kg)} / (\text{serum creatinine [mg/dL]} \times 72)] \times 0.85$
 - i. Urine protein/creatinine ratio (UPCR) \leq 1 mg/mg (\leq 113.2 mg/mmol).
7. Capable of understanding and complying with the protocol requirements and must have signed the informed consent document.
8. Sexually active fertile subjects and their partners must agree to use medically accepted methods of contraception (eg, barrier methods, including male condom, female condom, or diaphragm with spermicidal gel) during the course of the study and for 4 months after the last dose of study treatment.
9. Female subjects of childbearing potential must not be pregnant at screening. Females of childbearing potential are defined as premenopausal females capable of becoming pregnant (ie, females who have had any evidence of menses in the past 12 months, with the exception of those who had prior hysterectomy). However, women who have been amenorrheic for 12 or more months are still considered to be of childbearing potential if the amenorrhea is possibly due to prior chemotherapy, antiestrogens, low body weight, ovarian suppression or other reasons.

Exclusion Criteria

1. Prior treatment with anti-PD-1/PD-L1 therapy, anti-CTLA-4 therapy or cabozantinib. Prior adjuvant anti-PD-1 and/or anti-CTLA-4 therapy is allowed if relapse is greater than 6 months from last dose.
2. Receipt of any type of small molecule kinase inhibitor (including investigational kinase inhibitor) within 2 weeks before first dose of study treatment.
3. Receipt of any type of cytotoxic, biologic or other systemic anticancer therapy (including investigational) within 4 weeks before first dose of study treatment.
4. Radiation therapy for bone metastasis or brain metastasis within 2 weeks, any other radiation therapy within 4 weeks before first dose of study treatment. Systemic treatment with radionuclides within 6 weeks before the first dose of study treatment. Subjects with clinically relevant ongoing complications from prior radiation therapy are not eligible.
5. Known brain metastases that are ≥ 10 mm or cranial epidural disease unless adequately treated with radiosurgery and/or surgery. Patients with treated brain metastases need to be asymptomatic (no neurologic symptoms or stable neurologic deficit) and off corticosteroids prior to start of treatment. If discontinuation of corticosteroids is not feasible due to post-radiation effects, asymptomatic patients on a stable dose of dexamethasone ≤ 2 mg daily (or equivalent) for ≥ 1 week prior to start of treatment will be permitted. Patients with active, asymptomatic brain metastases that are < 10 mm and no corticosteroid requirement will be permitted without radiosurgery or surgery based on nivo/ipi brain metastasis response data from Checkmate 204 [31]. Patients with active untreated brain metastases who are enrolled will require more frequent brain monitoring while on protocol. Refer to study schedule Table 7-1.
6. History of active autoimmune disorder requiring immunosuppressive agents. Patients with autoimmune disorders considered low risk, such as vitiligo and thyroiditis, will be allowed.
7. Concomitant anticoagulation with coumarin agents (e.g., warfarin), direct thrombin inhibitors (e.g. dabigatran), betrixaban, or platelet inhibitors (eg, clopidogrel).
Allowed anticoagulants are the following:
 - a. Prophylactic use of Low-dose aspirin for cardio-protection (per local applicable guidelines) and low-dose low molecular weight heparins (LMWH) are permitted.
 - b. Anticoagulation with therapeutic doses of LMWH or anticoagulation with direct factor Xa inhibitors rivaroxaban, edoxaban, or apixaban is allowed in subjects without known brain metastases who are on a stable dose of anticoagulant for at least 1 week before first dose of study treatment, and who have had no clinically significant hemorrhagic complications from the anticoagulation regimen or the tumor.
8. The subject has prothrombin time (PT)/INR or partial thromboplastin time (PTT) test $\geq 1.3 \times$ the laboratory ULN within 7 days before the first dose of study treatment.
9. The subject has uncontrolled, significant intercurrent or recent illness including, but not limited to, the following conditions:
 - a. Cardiovascular disorders:
 - i. Congestive heart failure New York Heart Association Class 3 or 4, unstable angina pectoris, serious cardiac arrhythmias.

- ii. Uncontrolled hypertension defined as sustained blood pressure (BP) > 150 mm Hg systolic or > 100 mm Hg diastolic despite optimal antihypertensive treatment.
 - iii. Stroke (including transient ischemic attack [TIA]), myocardial infarction (MI), or other ischemic event, or thromboembolic event (eg, deep venous thrombosis, pulmonary embolism) within 6 months before first dose.
 - b. Gastrointestinal (GI) disorders including those associated with a high risk of perforation or fistula formation:
 - i. The subject has evidence of tumor invading the GI tract, active peptic ulcer disease, inflammatory bowel disease (eg, Crohn's disease), diverticulitis, cholecystitis, symptomatic cholangitis or appendicitis, acute pancreatitis, acute obstruction of the pancreatic duct or common bile duct, or gastric outlet obstruction.
 - ii. Abdominal fistula, GI perforation, bowel obstruction, or intra-abdominal abscess within 6 months before first dose.
Note: Complete healing of an intra-abdominal abscess must be confirmed before first dose.
 - c. Clinically significant hematuria, hematemesis, or hemoptysis of > 0.5 teaspoon (2.5 ml) of red blood, or other history of significant bleeding (eg, pulmonary hemorrhage) within 12 weeks before first dose.
 - d. Cavitating pulmonary lesion(s) or known endotracheal or endobronchial disease manifestation.
 - e. Lesions invading or encasing any major blood vessels.
 - f. Other clinically significant disorders that would preclude safe study participation.
 - i. Serious non-healing wound/ulcer/bone fracture.
 - ii. Uncompensated/symptomatic hypothyroidism.
 - iii. Moderate to severe hepatic impairment (Child-Pugh B or C).
10. Major surgery (eg, GI surgery, removal or biopsy of brain metastasis) within 8 weeks before first dose of study treatment. Complete wound healing from major surgery must have occurred 1 month before first dose and from minor surgery (eg, simple excision, tooth extraction) at least 10 days before first dose. Subjects with clinically relevant ongoing complications from prior surgery are not eligible.
11. Corrected QT interval calculated by the Fridericia formula (QTcF) > 500 ms per electrocardiogram (ECG) within 28 days before first dose of study treatment [32].
Note: If a single ECG shows a QTcF with an absolute value > 500 ms, two additional ECGs at intervals of approximately 3 min must be performed within 30 min after the initial ECG, and the average of these three consecutive results for QTcF will be used to determine eligibility.
12. Pregnant or lactating females.
13. Inability to swallow tablets.
14. Previously identified allergy or hypersensitivity to components of the study treatment formulations.
15. Diagnosis of another malignancy within 2 years before first dose of study treatment, except for superficial skin cancers, or localized, low grade tumors deemed cured and not treated with systemic therapy.

16. Subjects with a condition requiring systemic treatment with either corticosteroids (> 10 mg daily prednisone equivalents) or other immunosuppressive medications within 14 days of study drug administration. Inhaled or topical steroids, and adrenal replacement doses > 10 mg daily prednisone equivalents are permitted in the absence of active autoimmune disease.

